11.1.10 ECG

Changes from baseline to each post-baseline visit (Week 0 [2 hours post-dose], Week 1, Week 2, Months 1, 3, 6, 9, 12, and 2 week follow-up) for ECG interval data and rate data will be derived as the post-baseline value minus the baseline value for the same assessment. Markedly abnormal values or changes from baseline will be identified.

For the new patients, baseline ECG values will be defined as the latest non-missing value collected prior to the first dose of study drug in this study (screening, Visit S1 or Week 0, Visit R1 [pre-dose]). For patients entering the study from a previous NKTR-118 study (D3820C00005 or D3820C00007), the primary baseline ECG values will be defined as the latest non-missing value collected prior to the first dose of study drug in the previous pivotal study (D3820C00004 or D3820C00005) (screening, Visit 1 or Week 0, Visit 3), and supportive baseline ECG values will be defined as the data collected at the final visit from the previous study.

11.1.11 Vital signs

Changes from baseline in vital signs (sitting blood pressure and pulse) at each post-baseline visit (Week 0 [1 hour post-dose], Week 1, Week 2, Months 1, 3, 6, 9, 12, and 2 week follow-up) will be derived as the post-baseline value minus the baseline value for the same assessment. Markedly abnormal values or changes from baseline will be identified.

For the new patients, baseline vital sign values will be defined as the latest non-missing value collected prior to the first dose of study drug in this study (screening, Visit S1 or Week 0, Visit R1 [pre-dose]). For patients entering the study from a previous NKTR-118 study (D3820C00005 or D3820C00007), the primary baseline vital sign values will be defined as the latest non-missing value collected prior to the first dose of study drug in the previous pivotal study (D3820C00004 or D3820C00005) (screening, Visit 1 or Week 0, Visit 3), and supportive baseline vital sign values will be defined as the data collected at the final visit from the previous study.

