- C-SSRS at screening (new patients only), randomization (obtained from last visit of the previous NKTR-118 study for rollover patients), and at each visit thereafter throughout the study, including the follow-up visit
- OIC Healthcare Resource Utilization assessed at selected time points throughout the study
- Recording of concomitant medications (other than laxative medication or opioid medication [maintenance and medication for breakthrough pain]) throughout the study
- Recording of AEs throughout the study, including the follow-up visit
- Recording of daily maintenance opioid regimen throughout the study, including the follow-up visit
- Recording of opioid medication for breakthrough pain throughout the study, including the follow-up visit. Note: Opioid breakthrough pain medication will be recorded on the relevant eCRF at Visit S1 for new patients (to cover medication taken during the previous 60 days). Information obtained at Visit S1 will be entered into the eDiary to facilitate eDiary recording. Between Visits S1 and R1 opioid breakthrough pain medication will be captured only in the eDiary. At all visits from Visit R1 on, opioid breakthrough pain medication will be recorded on the relevant eCRF for all patients.
- Recording of laxative medication throughout the study, including the follow-up visit (For NKTR-118 patients, bisacodyl use will be captured on the bisacodyl drug accountability eCRF).
- Routine safety laboratories (hematology, chemistry, and total cholesterol) and U/A and clinical assessments at screening (new patients only), randomization (obtained from last visit of the previous NKTR-118 study for rollover patients), and selected time points throughout the study
- ECG at screening (new patients only), randomization (initial ECG obtained from last visit of the previous NKTR-118 study for rollover patients; repeat ECG obtained in current study for all patients), and selected time points throughout the study
- Vital signs and physical examination at screening (new patients only), randomization (initial BP/pulse obtained from last visit of the previous NKTR-118 study for rollover patients, repeat assessment obtained in present study for all patients), and selected time points throughout the study

- Pregnancy test for WOCBP at screening (new patients only), randomization (obtained from last visit of the previous NKTR-118 study for rollover patients), and selected time points throughout the study

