- Complete physical examination (including rectal examination) for rollover patients (Note: this will be obtained from last visit of the previous NKTR-118 study, but must also include rectal examination). New patients will have a targeted physical examination (lungs, cardiovascular, abdomen) with weight. Special emphasis should be placed on the pre-randomization abdominal examination so as not to

enroll any patients with an acute abdominal process (see Section 4.2). At the discretion of the investigator, a rectal examination may also be performed for new patients, if necessary to ensure the safety of the patient.

- Pain level question (NRS) (average pain over the previous 7 days) will be completed.
- Sitting blood pressure and pulse must be measured (obtained from last visit of the previous NKTR-118 study for rollover patients). Please see Section 6.3.12.1 for additional details on the protocol-mandated methods for collection of vital signs. The accurate time in date, hours and minutes will be recorded for this measurement.
- 12-lead ECG after resting for 10 minutes, with triplicate ECGs collected over a 5-minute period. (obtained from last visit of the previous NKTR-118 study for rollover patients)
- Urine sample will be collected for urine pregnancy test (WOCBP). The urine pregnancy test result must be negative before the patient may continue with the visit and administration of study drug. Patients enrolling from a previous study will also have U/A and urine drug screen. (Urine pregnancy test, U/A, and urine drug screen will be obtained from last visit of the previous NKTR-118 study)
- Daily maintenance and breakthrough pain opioid dosing regimens will be asked about and recorded on the appropriate eCRFs. For patients who enter the study from a previous NKTR-118 study, the daily opioid and breakthrough pain dosing regimens will be confirmed by prescription or clearly labeled bottles of opioid medication. If a patient forgets to bring their medication prescription/bottle(s) to Visit R1, they will be asked to bring it to Visit R2.
- Laxative medication will be asked about and recorded on the laxative medication eCRF. (For NKTR-118 patients, bisacodyl use will be captured on the bisacodyl drug accountability eCRF).

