- Care should be taken to record heart rate and blood pressure, which at this visit should be performed 1 hour post-dose/after initial assessments. (For practical purposes, this can be performed and recorded within a window from 1 hour to 90 minutes post-dose/initial assessments).

Please see Section [6.3.12.1](#) for additional details on the protocol-mandated methods for collection of vital signs. The accurate time in date, hours, and minutes will be recorded for this measurement.

Additionally, if clinically significant decreases in blood pressure are noted at this post-dose/additional vital signs measurement, an additional measurement should be

taken approximately 2 hours later prior to the patient leaving the clinic (please refer to Section 6.3.12.1 for guidelines on management.)

In the event of clinically significant findings compared to the pre-dose/initial measurements (per the judgment of the investigator or delegate) please refer to Sections 5.8 and 6.3.13.3.

- Triplicate 12-lead ECGs will be obtained 2 hours after the dose of study drug (NKTR-118 patients) or 2 hours after initial assessments are completed (Usual Care patients).
- Modified Himmelsbach scale will be completed by the investigator 2 hours after the patient receives the dose of study drug (NKTR-118 patients) or 2 hours after initial assessments are completed (Usual Care patients).
- Study drug will be dispensed and dosing instructions will be provided (NKTR-118 patients only).
- A new supply of bisacodyl will be dispensed (NKTR-118 patients only).
- Patients will be given a home diary to record their use of breakthrough pain opioid medication and other concomitant medications between visits.
- An appointment for Visit R2 (Week 1) will be made. NKTR-118 patients will be instructed to bring study drug and unused bisacodyl with them to the visit.

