- v Sitting blood pressure and pulse must be measured at each specified visit, with accurate time in date, hours and minutes recorded. Additional details on protocol-mandated methods for collection of vital signs are specified in Section 6.3.12.1. At Visit R1, all patients will have blood pressure and pulse measured pre-dose/as an initial assessment. In addition, patients will have an additional blood pressure and pulse measurement performed 1 hour post-dose/after the initial assessment (for practical purposes, this can be performed within a window from 1 hour to 90 minutes post-dose). If clinically significant decreases in blood pressure are noted at this post-dose measurement, an additional measurement should be taken approximately 2 hours later, prior to the patient leaving the clinic. In the event of clinically significant findings compared to the pre-dose measurement (per the judgment of the investigator or delegate), please refer to Sections 5.8, 6.3.12.1, and 6.3.13.3 for additional guidelines on management.
- w Laxative medication will be asked about and recorded on the laxative medication eCRF. (For NKTR-118 patients, bisacodyl use will be captured on the bisacodyl drug accountability eCRF).

Figure 1 Study flowchart

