All laboratory test results, vital signs (sitting blood pressure and pulse), ECG results, body temperature, respiratory rate, and weight will be summarized for each treatment group using descriptive statistics at each visit for observed values and change from baseline.

The overall incidence, as well as shifts from baseline to each post-baseline visit, of potentially clinically significant laboratory test results, vital signs, ECG results, body temperature, respiratory rate, and weight will be summarized by treatment group. For visits where triplicate ECGs are obtained, the mean value of the 3 measurements will be used in the analysis.

Physical examination results (normal/abnormal by body system) will be summarized for each visit by treatment group. Changes from baseline in the physical examination results will be assessed using shift tables.

The proportion of patients with suicidal behavior and suicidal ideation throughout the study based on the C-SSRS will be presented for each treatment group. The proportion of patients within each of the 4 suicidal behavior categories and within each of the 5 suicidal ideation sub-categories will also be presented for each treatment group. Descriptive statistics on the total number of attempts, total number of interrupted attempts, and total number of aborted attempts will be summarized for each treatment group.

Total exposure to NKTR-118 25mg will be summarized combining the data from the current study with the exposure data from the previous NKTR-118 pivotal studies (D3820C00004 and D3820C00005).

Safety parameters may also be summarized by age group, gender, race, region, response to laxatives (LIR, non-LIR), and previous treatment with NKTR-118 (yes, no), as appropriate.

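### For rollover patients, the Week 0 post-dose change in ECG, blood pressure and pulse is taken from a pre-pivotal baseline, so the by-arm Week 0 row mixes a 1 to 2 hour change with one over about 12 or 24 weeks

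*Protocol*

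**What the plan says.** Section 11.1.11 derives "Changes from baseline in vital signs (sitting blood pressure and pulse) at each post-baseline visit (Week 0 [1 hour post-dose", and at the later visits. Section 11.1.10 does the same for ECG: "Changes from baseline to each post-baseline visit (Week 0 [2 hours post-dose", and so on to follow-up.

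Both sections define baseline by type of patient:

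- **New patients:** the last non-missing value before the first dose in this study, normally the R1 pre-dose reading.
- **Rollovers, primary:** for vital signs, "the primary baseline vital sign values will be defined as the latest non-missing value collected prior to the first dose of study drug", where the dose meant is the one that opened the patient's earlier pivotal trial (D3820C00004 or D3820C00005). The ECG wording is parallel.
- **Rollovers, supportive:** the final visit of the previous study.

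Neither section makes an exception for the Week 0 post-dose reading. Section 12.2 presents patients by the arm randomized in this study. Under Section 12.2.1, vital signs and ECG results "will be summarized for each treatment group using descriptive statistics at each visit for observed values and change from baseline".

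Section 12.2 also foresees three further summaries: rollover changes on both baselines, a new/rollover split, and a split by previous and current treatment. All three are qualified as applying where appropriate. The reason given for using both baselines is to see the effect of previous treatment.

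**The concern.** The R1 post-dose reading exists to show what happens in the first hour or two. Section 3.1.2.1 judges it against the same visit's first reading ("In the event of clinically significant findings compared to the pre-dose/initial measurements"), and footnote v of Table 1 does likewise ("In the event of clinically significant findings compared to the pre-dose measurement"). Section 3.1 pairs the two ECGs at that visit: "initial ECG obtained from last visit of the previous NKTR-118 study for rollover patients; repeat ECG obtained in current study for all patients".

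R1 is also the only visit with readings at a fixed time after a dose, because at later visits patients take their tablet before coming in (Section 3.1.2). Sections 1.4 and 6.3.13.3 explain why falls in blood pressure are of interest.

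Under the stated rule, the primary Week 0 change for a rollover also contains everything that happened since before the pivotal study. The within-arm mean, the spread and any count based on change from baseline then do not measure the acute change for these patients. Because the primary objective concerns NKTR-118 itself, the within-arm figures matter as well as the arm comparison.

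**Working it through.** **Interval covered by the Week 0 change**

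| Patient type | Primary baseline | Interval to the R1 post-dose reading |
|---|---|---|
| New | R1 pre-dose (normally) | 1 h (blood pressure, pulse) or 2 h (ECG) |
| Rollover from D3820C00005 | Before first pivotal dose | about 12 weeks |
| Rollover from D3820C00004 then D3820C00007 | Before first pivotal dose | about 24 weeks |

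The 12 and 24 weeks follow from Section 1.4. Section 3.1.2.1 makes R1 the same visit as the last treatment visit of the previous study, so a pre-dose reading from that visit exists for every rollover: "Sitting blood pressure and pulse must be measured (obtained from last visit of the previous NKTR-118 study for rollover patients".

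**Illustration of size, systolic pressure.** The protocol has no figure to reproduce. It does not state the rollover share, the SD, the correlations or the outlier criteria (the last are left to the SAP).

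Assumed inputs:
- SD 15 mmHg
- within-patient correlation ρ of 0.85 on the same day and 0.60 over 12 to 24 weeks
- rollover share w of 10%, 30% or 50%
- for the main figures, no mean drift before R1

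Arm sizes follow from 1135 patients at 2:1: 1135 × 2/3 ≈ 757 and 1135/3 ≈ 378.

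1. SD of change = √(2 × 15² × (1 − ρ)). New patients: √(450 × 0.15) = 8.22. Rollovers: √(450 × 0.40) = 13.42.
2. Pooled SD = √((1 − w) × 8.22² + w × 13.42²).
3. Standard error of the arm difference in mean change = SD × √(1/757 + 1/378) = SD × 0.0630.
4. Chance of a fall of 20 mmHg or more with no drug effect: Φ(−20/8.22) = 0.75% for new patients and Φ(−20/13.42) = 6.80% for rollovers, weighted by w.
5. The same with a true 5 mmHg fall on NKTR-118: Φ(−15/8.22) = 3.39% and Φ(−15/13.42) = 13.18%, weighted by w.

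| | R1 baseline for all | w = 10% | w = 30% | w = 50% |
|---|---|---|---|---|
| SD of Week 0 change (mmHg) | 8.22 | 8.87 | 10.06 | 11.12 |
| Ratio to 8.22 | 1 | 1.08 | 1.22 | 1.35 |
| SE of arm difference (mmHg) | 0.52 | 0.56 | 0.63 | 0.70 |
| Falls ≥20 mmHg, no effect | 0.75% | 1.35% | 2.56% | 3.77% |
| Falls ≥20 mmHg, 5 mmHg effect | 3.39% | 4.37% | 6.33% | 8.29% |
| Arm difference in falls (points) | 2.65 | 3.02 | 3.77 | 4.51 |
| That difference / its SE (unpooled) | 3.34 | 3.18 | 3.13 | 3.22 |

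Each 1 mmHg of mean drift in rollovers before R1 would shift the Week 0 mean of both arms by w × 1, that is 0.1, 0.3 or 0.5 mmHg.

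**Sensitivity.** With same-day correlation 0.80 to 0.90, long-interval correlation 0.50 to 0.65 and w from 10% to 50%, the SD ratio runs from 1.04 to 1.73. Chance falls run from 0.68% to 5.44%, against 0.14% to 1.75% with the R1 baseline.

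**The case against.** The strongest reply is that the protocol already holds the remedy. The rollovers' supportive baseline is the R1 initial reading, Section 12.2 foresees summaries on both baselines and by new/rollover status, and the remaining table choices belong to the SAP. This stands in part: the acute change can be recovered. But the supportive baseline is for rollovers only, is conditional, serves a different stated purpose and is not tied to Week 0. The primary rule for these named time points is fixed in the protocol, so it is not a matter left open for the SAP.

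A second reply is that a baseline before any NKTR-118 exposure is principled for a long-term safety study. That is right from Week 1 onward. It does not suit a reading taken 1 to 2 hours after a dose.

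A third is that the R1 baseline has its own mixture: for rollovers previously on NKTR-118 the R1 initial reading is an on-treatment value, and R1 is not their first exposure. That is true, but the mix of first and repeat doses is present under either baseline, and the previous-by-current split addresses it.

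Section 11.1.2 takes the R1 value as baseline for the pain NRS in all patients. This shows that the general rule can be varied by variable. It is a limited precedent, since it applies at every visit and may reflect the change from eDiary to clinic form.

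Several limits on the harm stand in full. Observed values and absolute-value criteria do not depend on the baseline. Drift before R1 precedes randomization, so the expected arm difference is unbiased. The study does no statistical testing.

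**Conclusion.** The point holds. As written, the primary by-arm Week 0 change for ECG, blood pressure and pulse mixes two different quantities, and for rollovers it is not the acute change.

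The consequence is modest. For the arm comparison the only cost is precision in mean change: under the assumptions above, a standard error 8%, 22% or 35% wider at a rollover share of 10%, 30% or 50%. Within each arm, the spread and the count of chance falls are inflated. The fall count uses the systolic drop alone. The full definition in Section 1.4 also requires systolic below 90, a diastolic drop of at least 10 and diastolic below 50 mmHg, which would remove most drift-only cases. No loss of ability to detect falls is claimed, since the ratio of difference to standard error stays between 3.1 and 3.3. Management of the patient at the visit is unaffected.

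The reading of the text is certain. The size rests on assumed SD, correlations and rollover share. The change is worth making because it costs almost nothing.

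**What to change.** Add one sentence to each of Sections 11.1.10 and 11.1.11: for the Week 0 post-dose time points only, baseline is the Visit R1 pre-dose/initial reading for all patients in both arms. Keep the existing primary baseline from Week 1 onward.

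Present the Week 0 change by the combinations of previous and current treatment already foreseen in Section 12.2, so that first-exposure and repeat-exposure patients can be told apart. A table footnote should state that Week 0 and later visits use different baselines for rollovers.

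No new data or procedures are needed, because the R1 initial readings are already collected for every patient.

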11.1.12 C-SSRS

Occurrence of suicidal behavior after baseline up to the final assessment (Visit R16) will be defined as having answered “yes” to at least 1 of the 4 suicidal behavior sub-categories (actual attempt, interrupted attempt, aborted attempt, and preparatory acts or behavior) at any post-baseline evaluation.

Occurrence of suicidal ideation after baseline up to the final assessment (Visit R16) will be defined as having answered “yes” to at least 1 of the 5 suicidal ideation sub-categories (wish to be dead, non-specific active suicidal thoughts, active suicidal ideation with any methods [not plan] without intent to act, active suicidal ideation with some intent to act [without

specific plan], and active suicidal ideation with specific plan and intent) at any post-baseline evaluation.

For the new patients, baseline C-SSRS will be defined as the latest non-missing value collected prior to the first dose of study drug in this study (screening, Visit S1 or Week 0, Visit R1). For patients entering the study from a previous NKTR-118 study (D3820C00005 or D3820C00007), the primary baseline C-SSRS will be defined as the latest non-missing value collected prior to the first dose of study drug in the previous pivotal study (D3820C00004 or D3820C00005) (screening, Visit 1 or Week 0, Visit 3), and supportive baseline vital sign values will be defined as the data collected at the final visit from the previous study.

11.2 Calculation or derivation of patient reported outcome variables

11.2.1 NRS for pain

See Section [11.1.2](#).

11.3 Calculation or derivation of health economic variables

11.3.1 Healthcare resource utilization

Healthcare resource utilization will be assessed as the number of healthcare visits per patient year for the management of their OIC, which will be calculated as follows:

$(\text{total number of visits/number of days on study drug}) \times 365.25$

The healthcare resource utilization will be summarized by type of OIC healthcare utilization category (healthcare practitioner, urgent care, ER).

12. STATISTICAL METHODS AND SAMPLE SIZE DETERMINATION BY ASTRAZENECA

12.1 Description of analysis sets

12.1.1 Safety analysis set

All randomized patients who received at least 1 dose of study drug (25 mg NKTR-118 or Usual Care) will be included in the safety analysis set. The safety analysis set will be used to assess safety and tolerability variables.

All major safety variables will also be presented by means of an outlier analysis. For labs, ECGs, and vital signs, these outlier criteria will be provided by the safety physician(s) and included in the SAP. For analyses such as modified Himmelsbach and NRS, generally accepted outlier criteria are not available but will be determined as appropriate before the time of database lock.

12.2.1 Safety analyses

Adverse events will be coded using the MedDRA dictionary. Three sets of AE summaries will be generated: (1) all AEs recorded in the clinical database, (2) all TEAEs (as defined in Section 11.1.1), and (3) AEs occurring after the last dose of study drug.

Number of events and proportions will be tabulated by preferred term and system organ class. An event that occurred 1 or more times on the date of or subsequent to first dose of study drug will contribute 1 observation to the numerator of the proportion. The denominator of the proportion will comprise all patients in the Safety analysis set. Adverse events will also be

summarized by intensity and separately, by causality (as determined by the investigator). Should a patient experience the same preferred term/system organ class within multiple intensity or causality categories, the patient's worst occurrence (most severe/most related) will be retained in the tabulations. Serious AEs and commonly occurring AEs will be summarized in a generally similar manner. Adverse events of special interest may be further summarized and analysis of AEs occurring within specific time periods (e.g. after 3 months, after 6 months, etc.) may be considered.

Adverse events, SAEs, AEs leading to death, and AEs leading to study discontinuation will be tabulated for each treatment group. Descriptive statistics for time to onset and duration of select AEs may be summarized by treatment group. Adverse events that could potentially be indicative of centrally mediated opioid withdrawal, abuse potential, and bowel perforation will be identified prior to database lock and will also be summarized by each treatment group.

The mean daily opioid dose will be summarized for the following intervals: randomization to Month 1, Months 1 to 3, Months 3 to 6, Months 6 to 9, and Months 9 to 12. The mean bisacodyl dose per week will be summarized only for the NKTR-118 treatment group using descriptive statistics for the following intervals: randomization to Month 1, Months 1 to 3, Months 3 to 6, Months 6 to 9, and Months 9 to 12. The observed composite modified Himmelsbach score and change from baseline will be summarized by treatment group at Week 1, Months 1, 3, 6, 9, and 12 using descriptive statistics. The observed score and change from baseline in the NRS pain scores (average in the 7 days prior to the study visit) will be summarized by treatment group for Weeks 1 and 2, Months 1, 2, 3, 6, 9, and 12.

All laboratory test results, vital signs (sitting blood pressure and pulse), ECG results, body temperature, respiratory rate, and weight will be summarized for each treatment group using descriptive statistics at each visit for observed values and change from baseline.

The overall incidence, as well as shifts from baseline to each post-baseline visit, of potentially clinically significant laboratory test results, vital signs, ECG results, body temperature, respiratory rate, and weight will be summarized by treatment group. For visits where triplicate ECGs are obtained, the mean value of the 3 measurements will be used in the analysis.

Physical examination results (normal/abnormal by body system) will be summarized for each visit by treatment group. Changes from baseline in the physical examination results will be assessed using shift tables.

The proportion of patients with suicidal behavior and suicidal ideation throughout the study based on the C-SSRS will be presented for each treatment group. The proportion of patients within each of the 4 suicidal behavior categories and within each of the 5 suicidal ideation sub-categories will also be presented for each treatment group. Descriptive statistics on the total number of attempts, total number of interrupted attempts, and total number of aborted attempts will be summarized for each treatment group.

Total exposure to NKTR-118 25mg will be summarized combining the data from the current study with the exposure data from the previous NKTR-118 pivotal studies (D3820C00004 and D3820C00005).

Safety parameters may also be summarized by age group, gender, race, region, response to laxatives (LIR, non-LIR), and previous treatment with NKTR-118 (yes, no), as appropriate.

